# 6.2 Statistical Analysis

# 6.2.1 **Primary endpoint**

Our primary hypothesis is that by providing anti-SARS-CoV-2 plasma, the rate of progression to mechanical ventilation or death will be decreased as compared to the rate in in the group receiving control plasma. We will apply a Fisher exact test to compare the combined endpoint of mechanical ventilation/death respiratory failure rates between the two groups occurring by day 15. 29. All analyses

will be conducted with a modified intention-to-treat approach, which excludes randomized subjects who do not initiate an infusion of the study plasma. As secondary analysis, we will also analyze the reduced oxygenation rate, requirement for supplemental oxygen rate, length of hospitalization, time to recovery (ordinal score 1-3) and mechanical ventilation rate, respectively, as well as occurrence of the primary endpoint by day 29 Statistical inference will be based on a two-sided Type 1 error rate of 0.05 and 95% confidence intervals.

Participants who are intubated for reasons other than hypercarbia/hypoxia, such as for a procedure or airway obstruction, will have ventilation settings evaluated to determine if need for ventilation due to hypoxia is meet. This will be determined by >12 hours of requirement for a mandatory mode of ventilation (volume control or pressure control) or Fi02 of > 40%. External adjudication of intubation for non-hypoxic/hypercarbic indication will be conducted.

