# 6 STATISTICAL PLAN

#### 6.1 Sample Size and Power Considerations

All power calculations were performed using Stata "power" package assuming a two-tailed  $\alpha$ =0.05. The planned sample size for the trial is 50 subjects, randomized in a 1:1 ratio to anti-SARS-CoV-2 convalescent plasma versus control plasma. The primary analysis will compare the combined endpoint of mechanical ventilation or death in the anti-SARS-CoV-2 convalescent plasma and control groups.

We base our sample size projection on the ACTT-1 data [22]They reported the progression within 15 days separately for COVID-19 hospitalized requiring supplemental oxygen and those requiring high flow oxygen or non-invasive ventilation. The proportion progressing were 20% and 34%, respectively in the standard of care group and 8% and 25% in the remdesivir group progression. For our assumption we assume a 32% progression rate on the standard of care (no convalescent plasma) In the absence of treatment with convalescent plasma, we anticipate that between 10 to 30% will experience the primary outcome of mechanical ventilation or death . Using the Fisher exact test: we will reject the null hypothesis under the data scenario in the Table below.

No. Mechanical ventilation/Death (%)	Control arm (%)	Active arm (%)
	5/25 (20%)	0/25 (0%)
	6/25 (24%)	<= 1/25 (4%)
	7/25 (28%)	<= 1/25 (4%)
	8/25 (32%)	<= 1/25 (4%)
	9/25 (36%)	<= 2/25 (8%)
	10/25 (40%)	<= 3/25 (12%)

Rejection Region for the Fisher Exact Test

We will use an 8-point ordinal scale to assess clinical status, based on WHO clinical trial guidance. We assume the same distribution of outcomes for the control arm (i.e., in the absence of treatment with

convalescent plasma) as in ACTT, as tabulated below. Assuming 25 participants are treated with convalescent plasma and 25 participants are untreated, we would have 80% power to detect a difference between treatment arms as follows:

Category	Control arm (%)	Active arm (%)
Death	12%	0
Hospitalized, on invasive mechanical ventilation plus additional organ support (pressors, RRT, ECMO)	0	0
Hospitalized, intubated and mechanical ventilation	20.0%	0
Hospitalized, on non-invasive ventilation or high flow oxygen devices;	12%	8%
Hospitalized, requiring supplemental oxygen fy mask or nasal prong	0	20%
Hospitalized, not requiring supplemental oxygen – requiring ongoing medical care (COVID-19 related or otherwise);	24%	12%
Not hospitalized, limitation on activities	16%	28%

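### The rejection table in 6.1 is not the Fisher exact test's region in three of six rows; separately, Fisher is valid but conservative at 25 per arm, and an unconditional exact test would recover some power

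*Combined protocol and SAP*

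**What the plan says.** Section 6.2.1 names the primary test: "We will apply a Fisher exact test to compare the combined endpoint" of mechanical ventilation or death between arms. It adds: "Statistical inference will be based on a two-sided Type 1 error rate of 0.05 and 95% confidence intervals". The analysis set is modified intention-to-treat and leaves out randomised patients whose infusion is never started.

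Section 6.1 fixes the size: "The planned sample size for the trial is 50 subjects, randomized in a 1:1 ratio", so 25 per arm. It gives a 32% control rate as the design assumption, then says "we anticipate that between 10 to 30% will experience the primary outcome of mechanical ventilation or death". It states no active-arm rate and no power for the primary endpoint. In place of power it says "Using the Fisher exact test: we will reject the null hypothesis under the data scenario in the Table below". The table lists, control vs active out of 25: 5 vs 0; 6 vs at most 1; 7 vs at most 1; 8 vs at most 1; 9 vs at most 2; 10 vs at most 3. The one power statement in 6.1 ("we would have 80% power to detect a difference between treatment arms as follows") belongs to the ordinal scale.

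Neither section mentions that the test is conservative, or an unconditional alternative.

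**The concern.** The table is the plan's only decision rule for the primary endpoint, and it is attributed to the test named in 6.2.1. If some of its rows are not rejections under that test, the plan holds two rules. A result in a disputed cell could then be called positive from the table and negative from the p-value. In a 50-patient trial with few events, such cells are not remote.

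The second question is efficiency. Fisher's test conditions on the total number of events. With few events its attainable error rates are coarse, so its true size can fall well below the nominal 5%. An unconditional exact test may then give more power with no extra patients.

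**Working it through.** **Inputs.** From 6.1: 25 per arm, two-tailed 0.05, control rate 32% (also 10 to 30%), and the printed table. From 6.2.1: Fisher's exact test. Assumed, because the plan gives none: active rates of 4% to 16% against 32%, and selected pairs at other control rates.

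**Step 1. Reproduce the printed table.** With equal arms the conditional distribution is symmetric. For a control and b active events (a>b, t=a+b) the two-sided p-value is

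p = 2 × Σ(k=0..b) C(25,k)·C(25,t−k) / C(50,t).

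- 5 vs 0: 2 × 53,130 / 2,118,760 = 0.0502
- 6 vs 1: 2 × (480,700 + 4,427,500) / 99,884,400 = 0.098
- 10 vs 3: 2 × 8,990,575,800 / 354,860,518,600 = 0.0507

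| Control events | Printed active limit | p at printed limit | True Fisher limit |
|---|---|---|---|
| 5 | 0 | 0.0502 | none |
| 6 | 1 | 0.098 | 0 |
| 7 | 1 | 0.0488 | 1 |
| 8 | 1 | 0.0232 | 1 |
| 9 | 2 | 0.0374 | 2 |
| 10 | 3 | 0.0507 | 2 |

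Three of six rows fail. Two of those p-values round to 0.05, but 0.098 does not. No variant tried gives the whole table. One-sided Fisher at 0.05 admits 6 vs 1, but also 8 vs 2 and 9 vs 3. Mid-p Fisher comes closest and misses only 6 vs 1 (0.076). Pearson and Yates chi-square also fail.

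**Step 2. How often the two rules would disagree.** Apply the printed limits to both arms symmetrically, with Fisher for all other outcomes. This region contains Fisher's, so the difference in rejection probability is the chance of a disputed outcome. At 32% control: vs 4%, 75.4 − 67.1 = 8.3 points; vs 8%, 51.9 − 45.4 = 6.5; vs 12%, 32.8 − 28.0 = 4.8; vs 16%, 19.5 − 16.3 = 3.2. The maximum size of this region is 3.9%.

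**Step 3. Size of Fisher at 25/25.** Sum the binomial probabilities of all rejecting outcomes at a common rate π:

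size(π) = Σ C(25,a)·C(25,b)·π^(a+b)·(1−π)^(50−a−b).

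Results: 0.88% at π=10%, 2.22% at 20%, 2.29% at 30%, 2.39% at 32%. The maximum over all π is 3.28%.

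**Step 4. Boschloo's test at 25/25.** Take the two-sided Fisher p-value as the ordering statistic and raise its cut-off as far as the maximum size over π stays within 5%. The cut-off is 0.079 and the maximum size 4.63%. The region holds every Fisher rejection and 24 more of the 26 × 26 = 676 outcomes. Among these, 5 vs 0, 8 vs 2 (Fisher p=0.074) and 10 vs 3 reject; 6 vs 1 does not.

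**Step 5. Power at 25/25**, by the same sum with separate rates per arm:

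| Control vs active | Fisher | Boschloo | Gain (points) |
|---|---|---|---|
| 32% vs 4% | 67.1% | 73.9% | 6.8 |
| 32% vs 8% | 45.4% | 54.1% | 8.7 |
| 32% vs 12% | 28.0% | 36.7% | 8.7 |
| 32% vs 16% | 16.3% | 23.5% | 7.2 |
| 30% vs 15% | 15.0% | 21.5% | 6.5 |
| 20% vs 4% | 23.0% | 31.3% | 8.3 |
| 20% vs 10% | 8.6% | 12.0% | 3.4 |
| 10% vs 5% | 1.3% | 3.2% | 1.9 |

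**Step 6. One patient fewer in one arm.** At 24/25 (control/active) or 25/24, Fisher's size at 32% is 3.35%. The gains at 32% vs 4%, 8% and 12% are 2.8, 4.2 and 5.4 points for 24/25, and 3.7, 3.7 and 4.3 for 25/24. Boschloo's cut-off at 24/25 is 0.062, not 0.079.

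**The case against.** The best defence is that Fisher's test is prespecified, named alike in 6.1 and 6.2.1, and valid at two-sided 0.05. Conservatism produces no false claim. Fisher controls error given the observed event total, whatever the final arm sizes. Boschloo's test controls it only unconditionally, under a two-binomial model, and its cut-off moves with the split. The choice between the two is a recognised matter of method. All of this stands.

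It also stands that the size of the gain depends on conditions the plan does not guarantee. A reader might infer that Fisher always spends less than half of the 5% here, or that 7 to 9 points are available in general. The documents do not support that. They give no active rate and also anticipate a 10 to 30% control rate, where the gain can be 2 to 3 points. The modified intention-to-treat set can also break the 25/25 split, and at 24/25 the size at 32% is above 2.5%.

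A reader might infer, too, that naming Boschloo's test would make the printed table correct. It would not: 6 vs 1 still fails, and 8 vs 2 would reject although the printed row stops at 1.

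None of this defends the table. Its row at 8 events, which matches the 32% assumption (8/25), is right, but three other rows are wrong for the test it is attributed to.

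**Conclusion.** The firm part is the table: three of its six rows are not rejections under the two-sided 5% Fisher test at 25 per arm. This follows from the plan's own figures without any assumed rate. A reader might infer that applying the printed rule would inflate the type I error. It would not, since its maximum size, extended as in step 2, is 3.9%. The fault is that two stated rules can give opposite verdicts on the primary endpoint.

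The choice of Fisher is not an error. Boschloo's test is a low-cost improvement worth about 7 to 9 points at exactly 25/25 and 32% vs an assumed 4-16%. The gain is about 3 to 5 points at 32% vs 4-12% after the loss of one patient from one arm, and 3.4 and 1.9 points at 20% vs 10% and 10% vs 5%. Nor does it rescue the design: for a halving from 32% to 16%, power goes only from 16.3% to 23.5%.

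**What to change.** **Required.** Regenerate the 6.1 table from whichever test 6.2.1 names. If Fisher stays, the limits at 25 per arm are: 5 vs none; 6 vs 0; 7 vs at most 1; 8 vs at most 1; 9 vs at most 2; 10 vs at most 2. State that the p-value from the named test on the realised arm sizes decides, and that the table is illustrative. The cost is a corrected table and one sentence.

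**Recommended.** Before any unblinded analysis, name Boschloo's test in 6.2.1. Specify its two-sided ordering statistic, compute the cut-off for the realised arm sizes, and add a matching exact interval for the risk difference. Report Fisher as a sensitivity analysis. The timing matters because section 7.4.1 has the safety monitoring committee reviewing unblinded data, including efficacy, during enrolment; the change should come from people who have not seen those data. The cost is SAP wording and a standard software routine. The downsides are a test less familiar to readers, and unconditional rather than conditional error control.

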# 3 PROTOCOL SUMMARY

Long title: A randomized controlled adaptive study comparing COVID-19 convalescent plasma (CCP) to non-immune plasma to limit coronavirus-associated complications in hospitalized patients.

Sample Size: n=50

**Study Population:** Hospitalized COVID-19 patients aged ≥18 years with respiratory symptoms and hypoxia, who do not currently require mechanical ventilation, enrolled within 3 days of admission to the hospital OR within 14 days of initial onset of symptoms.

Study Duration: May 25, 2020 to April 30, 2021

**Study Design**: This randomized, pragmatically blinded, placebo-controlled, adaptive trial will assess the efficacy and safety of anti-SARS-CoV-2 convalescent plasma in hospitalized patients with acute respiratory symptoms up to 14 days after the onset of initial symptoms.

A total of 50 eligible subjects will be randomized in a 1:1 ratio to receive either convalescent fresh frozen plasma from blood donors who have recovered from COVID-19 containing antibodies to SARS-CoV-2 or control (standard fresh frozen plasma collected prior to 12/1/2019 or with documented negative SARS-CoV-2 antibody). Should additional anti-COVID agents (anti-viral and/or anti-inflammatory) become available for use as standard of care during implementation, the sample size will be recalculated and increased to account for the estimated impact that these agents may have on the reducing the progression to the primary endpoint of severe hypoxemia.

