To evaluate the clinical efficacy of CCP relative to the control arm in adults hospitalized with COVID-19 according to clinical status (8-point ordinal scale) at Day 29	
 
Death;
 
Hospitalized, on invasive mechanical ventilation or ECMO;
 
Hospitalized, on non-invasive ventilation or high flow oxygen devices;
 
Hospitalized, requiring supplemental oxygen;
 
Hospitalized, not requiring supplemental oxygen - requiring ongoing medical care (COVID-19 related or otherwise);
 
Hospitalized, not requiring supplemental oxygen - no longer requires ongoing medical care;
 
Not hospitalized, limitation on activities and/or requiring home oxygen;
 
Not hospitalized, no limitations on activities.
 

OBJECTIVES	ENDPOINTS (OUTCOME MEASURES)
Additional Secondary Objectives	

 
To evaluate the clinical efficacy of different investigational therapeutics as compared to the control arm as assessed by:
 
Clinical Severity Ordinal scale:
 
Time to an improvement of one category and two categories from Day 0 (baseline) using an ordinal scale.
 
Subject clinical status using ordinal scale at Days 2,5,8,15, 29
 
Mean change in the ordinal scale from Day 1 to Days 2,5,8,15, 29
 
	
 
Clinical outcome assessed using ordinal scale daily while hospitalized and on Days 15, 29 and 120
 
Time to clinical recovery (defined as ordinal score 1-3)
 

 
National Early Warning Score (NEWS):
 
Time to discharge or to a NEWS of ≤ 2 and maintained for 24 hours, whichever occurs first.
 
Change from Day 1 to Days 2,5,8,15, 29
 
	
 
NEWS assessed daily while hospitalized
 

 
Oxygenation:
 
Oxygenation use up to Day 120.
 
Incidence and duration of new oxygen use during the study.
 
Oxygen requirement on day 1,2,5,8,15, 29
 
	
 
Days of supplemental oxygen (if applicable) up to Day 29
 
PaO2/FiO2 ratio or SpO2/FiO2
 
O2 requirement at day 120
 

 
Non-invasive ventilation/high flow oxygen:
 
Non-invasive ventilation/high flow oxygen use up to Day 29.
 
Incidence and duration of new non-invasive ventilation or high flow oxygen use during the study.
 
	
 
Days of non-invasive ventilation/high flow oxygen (if applicable) up to Day 29
 

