# 4.1.4 **Target population**

This study will enroll hypoxic hospitalized COVID-19 patients, a group that is at elevated risk for poor outcomes and progressive respiratory failure. To date, approximately 30-50% of hospitalized San Francisco COVID-19 patients have required intensive care level treatment, the majority due to respiratory failure[1]. This high progression to ICU level care due to respiratory failure has been seen across the US. This study targets patients who are still early in the course of disease, when CCP may be most effective, the "green zone" described in Figure 2. Once severe respiratory decompensation and ARDS occur and patients have progressed to the "red zone", CCP may be less effective, as was the case with use of CCP in SARS-1 -[8]. The study has been amended to include those on high flow nasal oxygenation, as well as those on nasal cannula. In the ACTT-1 study, 25% of participants on HFNC (ordinal group 6) progressed to mechanical ventilation or death [22] These individuals are at elevated risk of progression to intubation and it is important to understand if CCP can reduce deterioration of respiratory status.

This study will permit enrollment of pregnant women, breastfeeding women and women of childbearing potential. CCP should not pose a pregnancy specific risk, other than the known risks associated with blood product infusions in general. However, for pregnant or breastfeeding women, additional counseling will be provide as to the lack of data for CCP use in COVID-19 infection during pregnancy and lactation and that an adverse event that impacts the participant could also affect an unborn child by affecting maternal health. Pregnant women who chose to enroll will have the pregnancy outcome recorded.

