# 5 INVESTIGATIONAL PLAN:

# 5.1 Study objectives

OBJECTIVES	ENDPOINTS (OUTCOME MEASURES)
Primary Objective	
Evaluate the efficacy of convalescent fresh frozen plasma from blood donors who have recovered from Covid-19 containing antibodies to SARS-CoV-2 versus control (standard fresh frozen plasma) to prevent mechanical intubation within 14 days of CPP administration in hospitalized patients with COVID-19 who are within 3 days of hospital admission or 14 days of symptom onset.	Progression to mechanical intubation or death within the first 14 days of enrollment. A secondary endpoint will evaluate progression to endpoint within the first 28 days of enrollment.
Key Secondary Objectives	
To evaluate the clinical efficacy of CCP relative to the control arm in adults hospitalized with COVID-19 according to clinical status (8-point ordinal scale) at Day 29	
 
Death;
 
Hospitalized, on invasive mechanical ventilation or ECMO;
 
Hospitalized, on non-invasive ventilation or high flow oxygen devices;
 
Hospitalized, requiring supplemental oxygen;
 
Hospitalized, not requiring supplemental oxygen - requiring ongoing medical care (COVID-19 related or otherwise);
 
Hospitalized, not requiring supplemental oxygen - no longer requires ongoing medical care;
 
Not hospitalized, limitation on activities and/or requiring home oxygen;
 
Not hospitalized, no limitations on activities.
 

OBJECTIVES	ENDPOINTS (OUTCOME MEASURES)
Additional Secondary Objectives	

 
To evaluate the clinical efficacy of different investigational therapeutics as compared to the control arm as assessed by:
 
Clinical Severity Ordinal scale:
 
Time to an improvement of one category and two categories from Day 0 (baseline) using an ordinal scale.
 
Subject clinical status using ordinal scale at Days 2,5,8,15, 29
 
Mean change in the ordinal scale from Day 1 to Days 2,5,8,15, 29
 
	
 
Clinical outcome assessed using ordinal scale daily while hospitalized and on Days 15, 29 and 120
 
Time to clinical recovery (defined as ordinal score 1-3)
 

 
National Early Warning Score (NEWS):
 
Time to discharge or to a NEWS of ≤ 2 and maintained for 24 hours, whichever occurs first.
 
Change from Day 1 to Days 2,5,8,15, 29
 
	
 
NEWS assessed daily while hospitalized
 

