# 5.3 Study Population

# 5.3.1 Inclusion Criteria for Enrollment:

- 1. Patients ≥18 years of age
- 2. Hospitalized with COVID-19
- 3. Enrolled within 72 hours of hospitalization OR within day 14 from first signs of illness
- 4. Pulmonary infiltrates on chest imaging
- 5. Oxygenation of <95% on room air
- 6. Laboratory confirmed COVID-19

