# 8 point WHO ordinal Scale of clinical status[28]

# **Ordinal Scale for Clinical Improvement**

Patient State	Descriptor	Score
Uninfected	No clinical or virological evidence of infection	0
Ambulatory	No limitation of activities	1
	Limitation of activities	2
Hospitalized Mild disease	Hospitalized, no oxygen therapy	3
	Oxygen by mask or nasal prongs	4
Hospitalized Severe Disease	Non-invasive ventilation or high-flow oxygen	5
	Intubation and mechanical ventilation	6
	Ventilation + additional organ support – pressors, RRT, ECMO	7
Dead	Death	8

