# 6.2.2 Secondary endpoint (clinical status):

We will evaluate the clinical efficacy of CCP relative to the control arm in adults hospitalized with COVID-19 according to clinical status (8-point WHO ordinal scale) using a proportional odds model. Because clinical status is evaluated on multiple days, we will use a generalized estimating equations (GEE) approach to account for repeated measures within each patient. Changes in ordinal scale at each timepoint will be summarized by proportions.

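### Recovery defined as ordinal score 1-3 can already be met at enrolment on the only scale the protocol numbers, because entry does not require oxygen use; the unnumbered category list in the objectives tables conflicts with that scale

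*Combined protocol and SAP*

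**What the plan says.** **Endpoint.** The objectives tables (sections 3 and 5.1) list "Time to clinical recovery (defined as ordinal score 1-3"), and section 6.2.1 repeats the range as "time to recovery (ordinal score 1-3"). Neither place requires the score to be reached after baseline, limits the analysis to patients who start above 3, or says how a patient already at 3 is handled.

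**Entry.** Inclusion criterion 5, in both the summary and section 5.3.1, is "Oxygenation of <95% on room air". The summary describes the population as patients "with respiratory symptoms and hypoxia, who do not currently require mechanical ventilation". No inclusion criterion asks for supplemental oxygen, and no exclusion criterion removes patients who are not receiving it.

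**Scale.** The WHO table at the end of the study procedures is the only 8-point scale with scores attached. It gives 3 to "Hospitalized, no oxygen therapy". Section 6.2.2 analyses "clinical status (8-point WHO ordinal scale) using a proportional odds model". The objectives tables print another eight categories without numbers, starting with death. That list has two levels for hospitalized patients off oxygen: one still needing medical care, one not.

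**The concern.** On the numbered scale, the recovered range overlaps the range of allowed starting states. A patient with a saturation of, say, 94% on room air who has not been put on oxygen is eligible, scores 3, and meets the recovery definition at time zero. That event says nothing about plasma. It uses up a patient who could have contributed information, and chance differences between arms in the number of such patients add noise to the comparison. In a 50-patient trial a few such patients matter. If the rule is left open until the data are seen, the choice of how to handle them could also be influenced by the results.

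**Working it through.** The plan gives no power, event count or test for time to recovery, so there is no figure to reproduce. The check is mainly logical; the arithmetic only shows scale.

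**Step 1. Does the overlap exist?** Entry needs saturation below 95% on room air and does not need oxygen. Hospitalized without oxygen is score 3 in the WHO table. Recovery is 1-3. Since 3 lies inside 1-3, the definition is met at enrolment.

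**Step 2. Which scale does 1-3 refer to?**

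| Reading | Meaning of 3 | New inpatient off oxygen, needing care |
|---|---|---|
| WHO table (numbered 0 to 8) | in hospital, no oxygen | 3: recovered |
| Objectives list, counted best to worst | in hospital, no oxygen, care no longer needed | 4: not recovered |
| Objectives list, in printed order | non-invasive ventilation or high flow | 1-3 would be death, invasive ventilation and high flow: impossible as recovery |

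The ordinal table in section 6.1 has a single level for hospitalized patients off oxygen, third from best and worded as still needing care. That layout, and the wording of section 6.2.2, support the WHO reading.

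**Step 3. Weight of score 3 in the plan's own distribution (section 6.1).**
- Scores 1-3, control: 24 + 16 + 16 = 56%. Active: 12 + 28 + 32 = 72%. Difference: 16 points.
- Discharged only (scores 1-2), control: 16 + 16 = 32%. Active: 28 + 32 = 60%.
- So 24 points (control) and 12 points (active) of the recovered total are patients still in hospital and needing care.

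**Step 4. Dilution.** Let f be the share entering at score 3 (not in the documents). If all of them count as recovered and the 56% and 72% apply to the rest, the difference is (1 − f) × 16 points.

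| f | Recovered at baseline, of 50 | Difference (points) |
|---|---|---|
| 0% | 0 | 16.0 |
| 10% | 5 | 14.4 |
| 20% | 10 | 12.8 |
| 30% | 15 | 11.2 |

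**Step 5. Illustrative power.** All inputs except 25 per arm are assumptions: exponential recovery, control median 10 days, hazard ratio (HR) 2.2, whole-day times, censoring at day 28, two-sided log-rank test at 0.05.

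Hand check at f = 0:
- Recovered by day 28: 1 − 2^(−2.8) = 85.6% in control and 1 − 2^(−2.8 × 2.2) = 98.6% in active.
- Expected events: 25 × (0.856 + 0.986) = 46.
- z = √(46/4) × ln 2.2 − 1.96 = 3.39 × 0.788 − 1.96 = 0.71, which gives power of about 76%. Simulation gives about 75%.

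Simulated power with baseline score-3 patients counted as events at time zero, and the exact chance that two Binomial(25, f) counts differ by 3 or more:

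| f | Power, HR 2.2 | Imbalance of 3 or more |
|---|---|---|
| 0% | 75% | 0% |
| 5% | 71% | 10% |
| 10% | 65% | 23% |
| 20% | 54% | 37% |
| 30% | 45% | 44% |

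With HR 1.5, power goes from about 28% at f = 0 to about 22% at f = 10%. With HR 1.0, the rejection rate stays at about 5-6% for every f.

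**The case against.** **The other scale.** The 1-3 range appears in the same objectives table as the list that separates patients still needing care. Counted from best to worst, that list would put a newly admitted patient off oxygen at 4, and the overlap would largely go. This stands as a qualification. However, the protocol never numbers that list, and the scale it does number gives the overlap.

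**Such patients may be rare.** Section 4.1.4 says "The study has been amended to include those on high flow nasal oxygenation, as well as those on nasal cannula", and the progression rates in section 6.1 come from patients on supplemental oxygen, high flow or non-invasive ventilation. This also stands: f may be near zero. It is descriptive text, though, and excludes no one. A reader might infer from the objective "Incidence and duration of new oxygen use during the study" that the plan expects patients off oxygen at entry. The objective is compatible with that but does not prove it, because new use could include oxygen restarted after weaning.

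**The test is assumed.** Section 6.2.3 plans Kaplan-Meier curves with confidence bounds for time-to-event endpoints and names no log-rank test. The power figures therefore illustrate information lost; they do not describe a planned test.

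**Later deterioration.** A reader might add that a patient recovered at time zero who then worsens keeps the recovery. That is true of any first-occurrence endpoint and is not particular to score 3.

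**Conclusion.** The definition is wrong on the scale the protocol numbers, and ambiguous once the objectives list is taken into account. The logical gap needs no assumption about f.

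Its size does. Under the assumptions in step 5, the loss is about 4 points of power at f = 5%, 10 points at 10% and 30 points at 30%. It is smaller in absolute terms when the true effect is smaller.

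Two stronger readings are not supported. The chance imbalances might suggest a raised false-positive rate, but with no treatment effect rejection stays at about 5-6%, so the problem is dilution. The trial's main result might also seem to be at risk, but the primary endpoint, ventilation or death, does not use this score range. This is a correction to one secondary endpoint, worth making before unblinding.

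**What to change.** In section 6.2.1 and both objectives tables:

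1. Name the one scale to which score 1-3 refers, and bring the unnumbered list into line with it.
2. Define recovery as a post-baseline event that cannot be met at enrolment. On the WHO table there are two workable versions:
   - first post-baseline day at score 3 or less if baseline is 4-5, and at score 2 or less if baseline is 3; or
   - first post-baseline day at score 1-2 for everyone.

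The cost is a sentence or two and no new data, since the ordinal score is already recorded at enrolment. The first version pools two kinds of event: coming off oxygen for most patients, discharge for those starting at 3. The second avoids the pooling but makes recovery mean discharge for all. Power returns to about 75% under the first version only if baseline-3 patients reach discharge at the same rate as others reach score 3, which the documents do not establish. Neither version changes eligibility or treatment.
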